GCP	Good Clinical Practice
HREC	Human Research Ethics Committee
IC	Informed Consent
ICF	Informed Consent Form
IFU	Instructions for Use
IRB	Institutional Review Board
ISO	International Organization for Standardization

Acronym	Term
LAR	Legally Authorized Representative
MEC	Medical Ethics Committee
PI	Principal Investigator
PSR	Product Surveillance Registry
RA	Regulatory Authority
SADE	Serious Adverse Device Effect
REB	Research Ethics Board
SAE	Serious Adverse Event
US	United States of America
USADE	Unanticipated Serious Adverse Device Effect

3. Synopsis

Clinical Study Type	Post-Market Registry
Product Status	Medtronic market released products Instructions for Use (IFU) and/or product labelling provided in their respective manuals
Sponsor	Medtronic, Inc. Operational Headquarters [name] [name] Note: Medtronic, Inc. is the funding source for the Product Surveillance Registry
Local Sponsor	All Medtronic geographies and/or locations are listed under a separate cover
External Organizations	External organizations involved in the clinical investigation, if applicable, will be listed under a separate cover
Purpose/Overview	
Provide continuing evaluation and periodic reporting of safety and effectiveness of Medtronic market-released products for their intended useObtain real-world performance and safety information from a global network of hospitals, clinics, and clinicians intended to represent the range of clinical environments in which Medtronic products are usedSupport post-market surveillance activities and post-approval studies that are initiated by Medtronic, regulated by local governments, or are conducted to fulfill government and/or regulatory authority requestsObtain clinical evidence to guide the development and improvement of medical devices, therapies, device guidelines, and patient services/solutionsProvide clinical data to support health economics and clinical outcomes research
Objectives	Serve as an ongoing source of product performance, patient safety and clinical outcomes information associated with the use of market-released products. Objectives include: 
To identify device failures, adverse events or adverse event trendsTo characterize patient outcomes

	
• To characterize patterns of product use• To characterize predictors of performance and effectiveness• To identify potential signals for emerging performance issues
Study Design	Patient-centric, active post-market registry with an extensible design allowing products to be added following market release. Patients are enrolled and followed in accordance with the routine care practices of their care provider.
Eligibility Criteria	
Inclusion Criteria:
 
• Patient or legally authorized representative (LAR) provides authorization and/or consent per institution and geographical requirements• Patient has or is intended to receive or be treated with an eligible Medtronic product• Patient is consented within the enrollment window of the therapy received, as applicable 
Exclusion Criteria:
 
• Patient who is, or is expected to be, inaccessible for follow-up• Participation is excluded by local law• Patient is currently enrolled or plans to enroll in concurrent drug/device study that may confound the PSR results 
Note: Additional criteria may be required, refer to Condition/Therapy Appendix for further guidance.

Study Procedures and Assessments	Medtronic products are used to monitor, diagnose and/or treat many medical conditions. The PSR is an observational registry intended to collect data consistent with routine clinical care practices. In general, data collection includes: 
• Demographics• Medical History• Procedure Information• Patient Status• Adverse Events• Outcome Measures• Device Deficiencies 
In-person follow-up frequency is intended to align with routine clinical care practices consistent with real-world data collection.

However, in real-world clinical settings, routine care practices may vary for several reasons including but not limited to: physician preference, a patient's condition and/or personal circumstances; therefore, to mitigate potential bias and ensure a robust data set, sites are required to report patient status at regular intervals regardless of whether the patients are seen in-person.

Events are reported upon a site's first awareness throughout a patient's participation. Reportable events include:

- Device-Related Events
- Procedure-Related Events
- Therapy-Relevant Events¹

Note¹: Additional therapy-specific details may be provided in the Condition/Therapy Appendix.

4. Introduction

4.1. Background

Medtronic's commitment to quality is exemplified in our mission, "To strive without reserve for the greatest possible reliability and quality in our products; to be the unsurpassed standard of comparison and to be recognized as a company of dedication, honesty, integrity, and service." Consistent with this commitment, Medtronic has continually worked to develop systems and processes to more effectively monitor product performance following market release. Medtronic launched the global Product Surveillance Registry (PSR) in 2011, which was built on more than 25 years of post-market clinical surveillance experience to create a comprehensive product registry.

The PSR is sponsored by Medtronic and is comprised of a global network of hospitals, clinics and clinicians from which reliable real-world product safety and patient clinical outcome information is generated. It leverages a common infrastructure designed for the collection, analysis and dissemination of surveillance information for multiple Medtronic device technologies.

4.2. Purpose

The purpose of the PSR is to provide continuing evaluation and periodic reporting of safety and effectiveness of market-released products for their intended use. PSR data will support post-market surveillance activities and post-approval studies that are initiated by Medtronic, regulated by local governments, or are conducted to fulfill government and/or regulatory authority requests. The PSR will also obtain clinical evidence to guide the development and improvement of medical devices, therapies, device guidelines, patient services/solutions and provide clinical data to support health economics and

clinical outcomes research. Conducting product surveillance in populations over time provides an effective means of assessing product performance, patient safety and clinical outcomes. Product surveillance is the systematic collection, analysis, and interpretation of performance data, as well as its dissemination and application.

The PSR is designed to provide a repository of data for conducting signal detection activities for identification of emerging patient safety or performance issues. It is designed to obtain real-world performance and safety information from a global network of hospitals, clinics, and clinicians intended to represent the range of clinical environments in which Medtronic products are used. It provides a mechanism for gaining an increased understanding of the relationship between a product's performance and clinical outcomes, as well as improving patient safety by identifying potential performance trends.

The PSR data are intended to benefit and support interests of patients, hospitals, clinicians, regulatory bodies, payers, and industry by streamlining the clinical surveillance process and facilitating leading edge performance assessment via the least burdensome approach.

4.3. Eligible Products

Eligible products include market-released products. Approved indications of use for each market-released product are defined in the Instructions for Use (IFU) and/or product labelling. Not all Medtronic market-released products are eligible for enrollment. Product eligibility is based on the determination that there is an interest or requirement for obtaining additional information to further characterize product performance following market release. Medtronic may limit enrollment using an Enrollment Guide typically when the number enrolled is adequate to effectively assess product performance or product availability is restricted.

5. Objectives

5.1. Objectives

Conducting active post-market surveillance is dynamic. Therefore, the PSR is designed to adapt as technology, information, and/or requirements change with the capability of aggregating multiple surveillance data sources, providing increased value and utility in terms of product performance assessment. The objective of the PSR is to serve as an ongoing source of product performance, patient safety and clinical outcomes information associated with the use of market-released products.

Objectives include:

- To identify device failures, adverse events or adverse event trends

- To characterize patient outcomes
- To characterize patterns of product use
- To characterize predictors of performance and effectiveness
- To identify potential signals for emerging performance issues

6. Design

6.1. General

The PSR is designed to conduct active post-market surveillance. The PSR has an extensible design allowing products to be easily added following market release. Only patients treated with an eligible product can be enrolled, refer to Section 4.3. Data collection is intended to align with routine clinical care practice.

The PSR is patient-centric, following patients receiving one or more therapies over their continuum of clinical care. Sites may participate and contribute to the surveillance of multiple therapies. Sites are not required to participate in all PSR-supported conditions and/or therapies.

The PSR Platform Base CIP format has a modular design which provides a framework for the collection of surveillance data to support Medtronic's product portfolio. The PSR Platform Base CIP for a given Condition/Therapy is comprised of the following:

- PSR Core: defines elements applicable to all PSR patients, products, conditions, or therapies
- PSR Condition/Therapy Appendix: expands on the content of the PSR Core to further define specific procedure and data collection requirements for a given Condition/Therapy and is intended to align with routine care practices

The PSR Platform Base CIP is referred to as "CIP" throughout this document. The CIP for a given Condition/Therapy defines all minimum patient and site participation requirements (Refer to Figure 1).

Figure 1: PSR Platform Base CIP Modular Design

[figure not shown]
6.2. Analysis Requirements

Specific analysis requirements are documented, as applicable, and are integrated with the CIP in one of two ways, either via an associated Analysis Plan (AP) or Addendum (AD). Refer to the decision process provided in (Figure 2).

An AP, at a minimum, specifies the intended sample size estimates, analysis time points, reporting, etc. for a sub-population (and their data) from the overall PSR cohort of a given Condition/Therapy. The AP document can be specific to a patient population, therapy, product or product group and defines how the data will be analyzed. It does not contain any procedures or data collection requirements that differ from the CIP; therefore, an AP has no impact on the patient or how the site conducts PSR activities.

An AD can be specific to a patient population, therapy, product or product group, but unlike the AP, it does contain procedure and/or data collection elements that differ from the CIP. The AD describes the specific procedures that differ from the CIP (e.g., regulatory directed requirement), therefore an AD may impact the patient and/or how the site conducts PSR activities. An AD may have IRB/ Ethics Board, consent and potentially regulatory implications; therefore, additional site readiness activities may be needed, refer to Section 9.2. An AD includes, but is not limited to, unique procedure requirements, objectives/endpoints, statistical methodology, analysis cohort, and reporting timelines.

Figure 2: Decision tree for use of AP or AD

*Extensible Design: Supports Multiple Analysis Plans and/or Addendums

6.3. Steps Taken to Minimize Bias

Sites must meet pre-defined criteria to be selected to participate in the registry. The following methods may be incorporated to further minimize potential bias:

- Sites will consider enrollment of all eligible patients
- Enrollment may be limited at a site level by product and/or by therapy
- Events may be adjudicated by an independent review committee, as determined by therapy or regulatory requirements
- Diverse geographical site representation
- Sites represent various types of practice settings including university, community, public and private
- Data may be assessed by an independent reviewer (e.g., Core lab) as determined by therapy
- Procedures and data collection requirements are standardized

In addition, confounding variables and factors will be taken into consideration during data analysis, as applicable. Confounding variables and factors may include, but are not limited to:

- Medical history (e.g., comorbidities, surgical history)
- Patient-related factors (e.g., age, sex)
- Concomitant therapies

6.4. Duration

The duration of the registry may vary per Condition/Therapy and has no anticipated overall end date.

6.5. Rationale

The PSR is designed to conduct active post-market surveillance in populations over time providing an effective means of assessing product performance, patient safety and clinical outcomes. The PSR has an extensible design allowing products to be added on an on-going basis.

7. Product Description

7.1. General

Eligible products include Medtronic market-released products. Not all Medtronic market-released products are enrolled into the PSR. Product eligibility is based on the determination that there is an interest or requirement for obtaining additional information to further characterize product performance following market release.

8. Selection of Subjects

8.1. Registry Population

Patients are treated with an eligible Medtronic market-released product. The PSR supports active post market surveillance of multiple products used in the clinical care of numerous patient conditions for which Medtronic offers treatment.

8.2. Subject Enrollment

Enrollment of a patient is complete once the Informed Consent Form (ICF) or the Data Release Form (DRF) and an Authorization, if applicable, have been obtained. The following data will be collected at Enrollment:

- Consent (DRF or ICF) signature and date

If consent is waived, or is not required by local regulations, refer to the Condition/Therapy Appendix for patient enrollment information.

Patients are to be enrolled within an enrollment window defined by the therapy received. Refer to the Condition/Therapy Appendix for specific enrollment criteria. It is the site's responsibility to maintain a log of all patients enrolled in the registry. A consent/enrollment tracking tool may be provided to sites to assist in tracking the attempts to enroll eligible patients.

Retrospective patient enrollment may be allowed in certain instances. Refer to the Condition/Therapy Appendix for more enrollment details, if applicable.

8.3. Inclusion Criteria

- Patient or legally authorized representative (LAR) provides authorization and/or consent per institution and geographical requirements
- Patient has, or is intended to receive or be treated with, an eligible Medtronic product (Section 4.3)
- Patient is consented within the enrollment window of the therapy received, as applicable

Additional criteria may be required, refer to Condition/Therapy Appendix for further guidance.

8.4. Exclusion Criteria

- Patient who is, or is expected to be, inaccessible for follow-up
- Patient is excluded by local law
- Patient is currently enrolled in, or plans to enroll in, any concurrent drug/device study that may confound the PSR results (i.e. no required intervention that could affect interpretation of all-around product safety and/or effectiveness)

Additional criteria may be required, refer to Condition/Therapy Appendix for further guidance.

9. Site Selection and Readiness

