Patients may be enrolled prior to or after the surgical or medical procedure. Whether a particular cohort under this CIP enrolls patients before or after surgery or both, is defined in the applicable analysis plan or addendum. The site will make every attempt to approach all eligible patients for enrollment and

Medtronic Business Restricted

perform a thorough review of the patient's medical record to ensure requested baseline and medical history information is complete. When enrolling a patient before surgery, procedures are recommended to occur within 30 days of consent. When enrolling a patient after surgery, it is recommended to do so within 30 days following the procedure. If deemed necessary, the study team is allowed to deviate from those 30 days before or following surgery, provided justification in the applicable analysis plan or addendum.

If the patient is enrolled into the registry prior to the surgical or medical procedure but the procedure is not completed with an eligible product, the patient will be exited from the registry. The data that is to be collected on patients exited early will include the Enrollment CRF and the Exit CRF at minimum. Other CRFs, if collected, will be defined in the applicable analysis plan or addendum. No data will be collected after the patient is exited. Vulnerable patient populations such as pediatric patients may be enrolled when the use of the device is approved in the population and region per the applicable instructions for use (IFU). Regional requirements will be followed and described in the applicable analysis plan or addendum.

Sites may submit to their Ethics Board for a full waiver of consent if applicable. Patients at sites where the Ethics Board *has not* granted a full waiver of consent are considered enrolled once informed consent has been obtained. Patients at sites where the Ethics Board *has* granted a full waiver of consent are considered enrolled once the patient's eligibility is assessed and verified and the Enrollment CRF is complete. Relevant enrollment data collected for eligible patients include but are not limited to:

- Eligibility verification (i.e. Section 8.3 Inclusion Criteria and Section 8.4 Exclusion Criteria).

Study activities (e.g., data collection and entry) can only start after the patient is enrolled in the study.

B.2 Baseline

The following types of data may be collected at baseline for enrolled patients regardless of procedure performed:

- Demographics
- Medical History

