- Surgical History
- Vital signs
- Quality of Life or satisfaction measurements, if applicable

B.3 Procedure

The following types of data may be collected for enrolled patients as applicable for the procedure performed:

- Perioperative details
- Device details
- Adverse Events, Device Deficiencies, Deaths, and deviations are to be reported to Medtronic upon awareness
- Imaging, if applicable
- Procedure recordings, if applicable
- Quality of Life or satisfaction measurements, if applicable

[figure not shown]
[figure not shown]
B.4 Follow-up Reporting Frequency & Data Collection

Patients will be treated in accordance with the routine clinical practices of their respective care provider. However, in 'real world' clinical practice, the frequency of in-person follow-up visits may vary for many reasons (e.g., patient's personal circumstances, condition, physician preference, etc.) resulting in more or fewer in-person visits.

As a result, the PSR is based on an active surveillance model which requires sites to complete a patient status assessment post-procedure, regardless of whether the patient is seen in-person per the physician's routine follow-up care practices. This approach ensures a robust dataset while increasing the continual awareness of patient status throughout their registry participation.

Data will be captured through 30 days post-procedure (to be reported between day 30 and 37) at a minimum and may be captured up to 60 months (or 5 years) post-procedure (Figure 1).

For procedures requiring long-term follow-up data, assessments will be collected at least annually with a maximum follow-up duration of 60 months at which time the patient will be exited (Figure 1). The total duration of follow-up for products requiring long-term follow-up data collection will be determined by various factors including but not limited to product lifecycle, recurrence rate, or regulatory requirements. The timing of the patient assessments and exit will be outlined in the corresponding Analysis Plan or Addendum. Refer to Figure 2 for an example of a long-term follow-up data collection schedule.

Surgical Appendix - Figure 1: Follow-up Schedules**Surgical Appendix - Figure 2: Example of a Long-term Schedule**

Follow-up data will be collected for enrolled patients and may include, but are not limited to:

- Patient status
- Readmissions
- Imaging information, if applicable
- Procedure recordings, if applicable

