Surgical Appendix - Table 3: Definitions for Event Severity

Event type	Severity Definition
Mild event	Signs, or symptoms that are easily tolerated by the subject, or are clinical or diagnostic observations of the investigator.
Moderate event	Signs, or symptoms that cause discomfort and interfere with normal functioning. Local or non-invasive intervention may be indicated.
Severe event	Signs, or symptoms that disable the subject, are medically significant, lead to hospitalization or prolongation of hospitalization.

B.6 Lost to Follow-up

Follow-up data may be collected via medical record review within the expected reporting period. In cases where a subject interaction is required for a study endpoint, subjects may be considered lost to follow-up if at least two attempts to contact the subject are unsuccessful. The method of attempt (e.g., one letter and one phone record, or two letters) must be documented in the subject's source documentation. In addition, regulation set forth by the governing EC/IRB must be followed.

B.7 Exit

Enrolled patients will be exited from the registry once the applicable duration of follow-up has been completed unless exited early for unavoidable reasons. Patients with an ongoing reportable Adverse Event or Device Deficiency at the time of final registry timepoint will be followed until resolution for up to 30 days after the final registry timepoint, or other applicable period as defined in the analysis plan or addendum.

B.8 Schedule of Data Collection

Surgical Appendix - Table 4: Data Collection Schedule

	Enrollment and Baseline	Procedure	Follow-up Assessment
Informed Consent, if applicable	X		
Patient status		X	X
Demographics and Medical and Surgical History	X		
Vital signs	X	X	X
Procedure information		X	
Imaging, if applicable	X	X	X
Product and/or therapy information, if applicable	X	X	X
Quality of Life or satisfaction measurements, if applicable	X	X	X
Readmission			X
Reintervention		Reported upon site awareness	
Procedure/Device Related Adverse Events		Reported upon site awareness	
Device Deficiencies		Reported upon site awareness	
Deaths		Reported upon site awareness	
Deviations	Reported upon site awareness		

C. Data Collection Details

Data collection details and CRFs (where required) are provided under separate cover.

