### 5.4.2 Exclusion Criteria

- Subject who is, or is expected to be, inaccessible for follow-up
- Subject is excluded by local law
- Subject is currently enrolled in, or plans to enroll in, any concurrent drug/device study that may confound the PSR results (i.e. no required intervention that could affect interpretation of all-around product safety and/or effectiveness)

Additional criteria may be required, refer to Condition/Therapy Appendix for further guidance.

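### In cohorts enrolled after the procedure, the inaccessible-for-follow-up exclusion can be judged once primary-endpoint events are known, so selection into the primary event rate can depend on the outcome

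*Protocol*

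**What the plan says.** Protocol 8.4 excludes a "Patient who is, or is expected to be, inaccessible for follow-up", and SAP 5.4.2 repeats it: "Subject who is, or is expected to be, inaccessible for follow-up". Neither gives a reference time.

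On timing, Surgical Appendix B.1 says: "Patients may be enrolled prior to or after the surgical or medical procedure". The choice is made elsewhere: "Whether a particular cohort under this CIP enrolls patients before or after surgery or both, is defined in the applicable analysis plan or addendum". The window is a recommendation: "When enrolling a patient after surgery, it is recommended to do so within 30 days following the procedure". The analysis plan (AP) or addendum (AD) may justify a different one. Eligibility is verified against Protocol 8.3 and 8.4 whichever route is used. At sites with a full waiver of consent, patients "are considered enrolled once the patient's eligibility is assessed and verified and the Enrollment CRF is complete".

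SAP 7.9.1.2 sets the short-term primary endpoint as the related-event rate after the procedure or within 30 days of it. SAP 7.1.3 requires every member of any analysis set to meet all the criteria, and SAP 7.9.1.3 repeats that condition for the primary rate.

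On follow-up, Appendix B.4 describes a model that "requires sites to complete a patient status assessment post-procedure, regardless of whether the patient is seen in-person", and B.6 adds: "Follow-up data may be collected via medical record review within the expected reporting period".

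**The concern.** For a patient enrolled before surgery, the criterion is a baseline judgement. For a patient enrolled afterwards, the site applies the same words with the post-operative course in view, possibly after most of the endpoint window has passed. The most plausible case is a patient transferred to another hospital after a complication, whom the site now considers out of reach. If that patient is excluded, the event disappears from the primary rate along with the patient.

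The loss would also be hard to see. Protocol 8.2 requires a log of enrolled patients only; the tracking tool is optional and concerns attempts to enrol eligible patients. SAP 7.1.1 defines an enrolled subject as one who meets all criteria, so disposition tables need not show these exclusions. The bias safeguards in Protocol 6.3 and SAP 7.3 speak of eligible patients, which leaves out those the criterion removes. SAP 6.2 nonetheless describes the registry sample as representative. A larger sample does not cure a selection effect of this kind.

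**Working it through.** **The plan's own figures.** SAP 6.1 uses N = 1.96² × p(1 − p) / h², with h the half-width. For p = 10% and h = 5%: 3.8416 × 0.09 / 0.0025 = 138.30, rounded up to 139, as tabulated. All nine tabulated sizes reproduce. They are not in dispute and do not change; the 5-point half-width serves only as a yardstick.

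**The chain in the text.**
1. The criterion has no reference time (Protocol 8.4, SAP 5.4.2).
2. It is applied unchanged to post-procedure enrolment, recommended within 30 days (Appendix B.1).
3. That window overlaps the short-term endpoint window of up to 30 days (SAP 7.9.1.2).
4. Failing it removes the patient from numerator and denominator (SAP 7.1.3, 7.9.1.3).

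Nothing in the Protocol, Appendix or SAP ties the judgement to the procedure date.

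**Effect on the rate.** Let p be the true rate, q the share of event patients excluded as inaccessible, and r the share of event-free patients excluded. Then

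observed rate = p(1 − q) / [p(1 − q) + (1 − p)(1 − r)].

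The documents give neither q nor r; all values below are assumptions. With p = 10%, r = 2% and the whole cohort enrolled after surgery, per 100 procedures (90 × 0.98 = 88.2 event-free patients retained):

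| q | Calculation | Observed rate | Shift (points) |
|---|---|---|---|
| 10% | 9 / (9 + 88.2) | 9.26% | −0.74 |
| 20% | 8 / (8 + 88.2) | 8.32% | −1.68 |
| 30% | 7 / (7 + 88.2) | 7.35% | −2.65 |

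The last shift is 2.65 / 5 = 53% of the 5-point half-width.

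**Direction.** If q = r, the observed rate equals p. If q < r, it rises: q = 0 and r = 5% gives 10 / (10 + 85.5) = 10.47%; q = 2% and r = 10% gives 9.8 / (9.8 + 81) = 10.79%.

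**Mixed cohorts.** If half the analysed patients were enrolled before surgery and are unaffected, the three downward cases become (10 + 9.26)/2 = 9.63%, (10 + 8.32)/2 = 9.16% and (10 + 7.35)/2 = 8.68%.

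**Confidence interval.** With r = 0 and the whole cohort enrolled after surgery, the chance that an exact binomial 95% interval contains the true rate is:

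| True rate, N | q = 0 | q = 10% | q = 20% | q = 30% |
|---|---|---|---|---|
| 10%, 139 | 96.8% | 96.6% | 94.0% | 88.1% |
| 20%, 246 | 96.2% | 92.4% | 77.7% | 50.2% |

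**The case against.** A reader might infer that patients with complications are excluded as the rule stands and that the primary rate is therefore biased low. The documents do not support that.

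- **Few patients meet the criterion.** It concerns access for follow-up, and follow-up may be by record review (Appendix B.6), by telephone, telehealth, email or mail (Protocol 10.6.2), or by a status report without a visit (Appendix B.4). A patient in intensive care at the enrolling site is accessible, and one in institutional care usually can be reached. Protocol 10.3 provides for seriously ill or unconscious patients, and 8.3 allows consent by a legal representative. This largely stands. Transfer elsewhere, with records or contact failing, is the example that survives. The follow-up provisions are not, however, tied to how 8.4 is to be judged, so sites may differ.
- **The direction is not established.** A patient with a complication may be readmitted or seen more closely, while a well patient may never return. This stands: the sign depends on q against r.
- **The exposure may be small or absent.** Only cohorts whose AP or AD permits post-procedure enrolment are affected, and only through events before enrolment or a prognosis already evident then. Those documents are not available here. This stands, but no text in the platform documents prompts an AP or AD author to fix the reference time.
- **Genuine inaccessibility matters for long follow-up.** Follow-up may run to 60 months. SAP 7.4 analyses observed data, while the 7.9.1.3 denominator counts everyone eligible, enrolled and operated on. Enrolling unreachable patients without further provision could count unseen events as none. This stands, and the fix has to deal with it.

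**Conclusion.** The structural point holds. In cohorts enrolled after the procedure, an eligibility criterion can be judged with knowledge of the outcome, and the primary rate is conditioned on it. I found no rule or record that would prevent or reveal this.

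What follows is a risk of bias of unknown sign and size. It is downward if event patients are judged inaccessible more often than event-free patients, absent if the shares are equal, and upward in the reverse case. The range from 9.3% to 7.4% for a true 10% assumes that the whole cohort is enrolled after surgery, that 2% of event-free patients are excluded, and that 10% to 30% of event patients are excluded. It is illustrative, and its lower end rests on the most extreme assumption. Cohorts enrolled only before surgery are unaffected.

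**What to change.** In Surgical Appendix B.1 and SAP 5.4.2, state that for patients enrolled after the procedure:

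- this criterion is judged only on circumstances present before the procedure;
- an event, transfer, prolonged stay or discharge destination arising after the procedure is not a ground for exclusion.

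In SAP 7.4 and 7.9.1.3, state that events already documented at enrolment count in the primary rate. Patients whose status through the endpoint time cannot be obtained are to be reported as having incomplete follow-up and not silently counted as event-free.

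Where the criterion is still applied after surgery, keep only a non-identifying count by reason, for example in the enrolment tracking tool, as far as local rules allow. Appendix B.1 does not permit study data collection before enrolment, so nothing more should be asked about patients who are never enrolled.

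The cost is Appendix and SAP wording plus site training. The downside is a few more enrolled patients with incomplete follow-up or needing records from another hospital. Sample sizes do not change.
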